9.6.2. Record Retention

To enable evaluations and/or inspections/audits from regulatory authorities or Pfizer, the investigator agrees to keep records, including the identity of all participating patients (sufficient information to link records, e.g., eCRFs and hospital records), all original signed informed consent documents, copies of all eCRFs, safety reporting forms, source documents, detailed records of treatment disposition, and adequate documentation of relevant correspondence (e.g., letters, meeting minutes, and telephone call reports). The records should be retained by the investigator according to local regulations or as specified in the clinical study agreement, whichever is longer. The investigator must ensure that the records continue to be stored securely for so long as they are retained.

If the investigator becomes unable for any reason to continue to retain study records for the required period (e.g., retirement, relocation), Pfizer should be prospectively notified. The study records must be transferred to a designee acceptable to Pfizer, such as another investigator, another institution, or to an independent third party arranged by Pfizer.

Investigator records must be kept for a minimum of 15 years after completion or discontinuation of the study or for longer if required by applicable local regulations.

The investigator must obtain Pfizer's written permission before disposing of any records, even if retention requirements have been met.

9.7. Data analysis

Detailed methodology for summary and statistical analyses of data collected in this study will be documented in a separate statistical analysis plan (SAP), which will be dated, filed and maintained by the sponsor. The SAP may modify the plans outlined in the protocol; any major modifications of primary endpoint definitions or their analyses would be reflected in a protocol amendment.

Analyses will be performed by pH Associates using Stata (StataCorp LLC) and R. Data from all participating centres will be pooled for analysis.

According to the objectives, descriptive statistics will be presented using data at 1 year (using retrospective data collected) or 2 and 3 years (using the prospective data as well as the retrospective data collected) following initiation of palbociclib. Clinical measurements will be presented at each time-point available, as described in section 7.3. The interim study report will only present results for objectives which are relevant to the 1-year follow-up period and the final report will present results for objectives which are relevant up to the 3-year follow-up period.

Descriptive statistics (numbers, percentages, means, standard deviations [SD], medians, quartiles, minimum, and maximum), as appropriate to the data collected, will be used to describe baseline demographic and clinical characteristics for the overall study. Treatment patterns and hospital admissions will also be reported using descriptive statistics. The frequency and proportion of patients experiencing a neutropenia, febrile neutropenia event;

and gastro-intestinal toxicity including diarrhea, nausea and vomiting, during follow-up, will be presented.

Definitions will be implemented as described in section 9.3 Variables. Patients who are known to be alive at the date of data collection (1-year for interim report and 3-year for full study report) will be censored at the date of data collection, and patients who are lost to follow-up will be censored on the date they were last known to be alive (e.g. date of last recorded hospital visit). Patients who are alive and free from disease progression at the date of data collection and those lost to follow-up will be censored on the date they were last known not to have disease progression (i.e. the date of last documented response assessment). Patients remaining in CR or PR at the end of the post-initiation observation period or lost to follow-up will be censored on the date CR or PR was last documented.

For the estimation of the proportion of patients alive, and free from disease progression, the denominator will be all patients known to be alive at the selected time-points (1 years, 2 years and 3 years). For the estimation of the proportion of patients achieving PR, CR and with stable disease at the selected time-points (1 years, 2 years and 3 years), the denominator will be all patients with at least one assessment of response (CR / PR / no response or stable disease / progressive disease) in the past year. Estimation of time to achieving best overall response and duration of response; and representation using swimmer plots will be performed in patients who respond (achieve CR or PR during follow-up) only.

Median PFS, OS, time to achieving best overall response, time to palbociclib dose modification and time to palbociclib discontinuation, and corresponding 95% CIs, will be estimated using Kaplan-Meier curves. Assessments of response (CR / PR / no response or stable disease / progressive disease) in patients responding to treatment (achieving CR or PR following initiation of palbociclib) will be represented using “swimmer plots”.

All percentages will be reported to the nearest whole number; therefore, in reporting study results in tables, figures and associated text, percentages may not add up to 100% due to rounding.

Where dates are ambiguous because of missing day and/or months, standard imputation will be applied: where day is missing the 15th of the month will be assumed; where both day and month are missing the 1st of July will be assumed unless data collected is in 2017 (year of initiation of IPP) in which case the 15th of August will be assumed (midpoint as IPP was initiated in April 2017). Where other types of data are missing from the original medical record, the affected analyses will be conducted using only the results of those patients with data available and the number included in each analysis will be stated. The percentage of data missing will be reported for each study variable. The calculation of percentages will not contain the missing categories. Counts of missing observations will be presented in a separate category.

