9.1. Study design

This study will be a UK-wide, multi-centre, non-interventional cohort study (Figure 1). The study will involve secondary use of hospital medical records (paper-based or electronic, as

appropriate), collected both retrospectively and prospectively, from patients' medical records. Data will be collected for a maximum of 3 years following enrollment into the IPP.

[figure not shown]
Consent from living patients will be required if data are collected by pH Associates. In that case, patients will be provided with information about the study and approached for consent by members of the direct care team, either by post or in person at a routine hospital visit. Since no consent can be obtained if the patient is deceased, identifiable medical records of deceased patients will be accessed for study data collection by the direct care team only, to preserve confidentiality and avoid bias arising from exclusion of deceased patients.

Data will be collected retrospectively from the point of patient's enrollment into the IPP until initial data collection, expected to take place between November 2018 and February 2019. Members of the direct care team, or researchers from pH Associates (for living patients only), will collect existing (retrospective) data from the medical records of eligible patients in an electronic case report form (eCRF).

After the initial retrospective data collection, data will be collected prospectively up to a maximum of 3 years from enrollment in the IPP by members of the direct care team by updating the eCRF with any subsequent therapeutic and progression data available in the medical records until the end of the 3 year follow-up period.

The palbociclib initiation date will be defined as the index date. The baseline period will extend from the date of diagnosis up to palbociclib initiation (index date). The post-initiation observation period will be defined as the period from the index date until the end of the 3 year follow-up period. Patients will contribute data up to the time that they are lost to follow-up (for example due to discharge, death or other reasons) or 3-year post-index observation period, whichever is sooner.

Figure 1. Schematic of study design

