Secondary Objective 2: To describe overall survival and progression-free survival, response (CR, PR), stable disease. This includes estimating the proportion of patients achieving those endpoints at 1, 2 and 3 years following palbociclib initiation; median survival, time to response and duration of response. In patients who respond to treatment, to describe PR and CR using "swimmer plots".

- Proportion of patients at 2-years following initiation of palbociclib who:
 - Are free from disease progression.
 - Are alive
 - Achieved PR
 - Achieved CR
 - Had stable disease
- Median (95% confidence interval [CI]):
 - PFS

PFIZER CONFIDENTIAL

- OS
 - Time to achieving best overall response
- Length of follow-up
- Best response to palbociclib, overall and by de novo and relapse status
- Time to best response – by de novo and relapse status
- Time to first response – overall and by de novo and relapse status

Secondary Objective 3: To describe the occurrence of neutropenia during the first-year post-initiation observation period.

- In the 6 months post-palbociclib initiation, proportion of patients who experience,
 - Neutropenia (overall and by grade, recorded and inferred from ANC measurements).
 - Worst neutropenia experienced within 3 months of palbo initiation
 - Febrile Neutropenia.

[figure not shown]
Secondary Objective 4: To describe the occurrence of gastro-intestinal toxicity, including diarrhoea, nausea and vomiting during the first-year post-initiation observation period.

- For each cycle, proportion of patients who experience Gastro-intestinal toxicity, including:
 - Diarrhoea.
 - Severity
 - Nausea.
 - Severity
 - Vomiting.
 - Severity
- Proportion of patients experiencing an AE during follow-up

Secondary Objective 5: To describe progression of clinical indicators, including biochemical and radiological indicators at each time-point available during the first year following palbociclib treatment initiation.

- Summary measures of full blood counts in the first 6 months following initiation:
 - Haemoglobin.
 - White cell counts.
 - Absolute neutrophil counts.
 - Platelet counts.
- Summary measures of liver function tests in the first 6 months following initiation:
 - aspartate transaminase (also called aspartate aminotransferase).
 - alanine transaminase (also called alanine aminotransferase).
 - alkaline phosphatase.
 - Albumin
 - Bilirubin

PFIZER CONFIDENTIAL

[figure not shown]

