- Summary measures of bone profile in the first 6 months following initiation:
 - Calcium.
 - Phosphate.
- Summary measures of urea and electrolytes in the first 6 months following initiation:
 - Creatinine
 - Potassium
 - Sodium
 - Urea
- Summary measures of radiological indicators in the first 6 months following initiation including the proportion of patients with:
 - Stable disease.
 - Progressive disease.
 - CR or PR.

Secondary Objective 6: To describe BC-related healthcare resource utilisation during the first year following palbociclib initiation.

- Summary measures of hospital admissions for each line of therapy, including:
 - Proportion of patients with at least one inpatient admission recorded
 - Inpatient admissions per patient.
 - Elective or non-elective.
 - Reasons for admission (including day cases).
 - Length of stay per inpatient admission.
 - Proportion of patients with at least one outpatient visit recorded
 - Outpatient visits per patient.
 - Reason for outpatient visit
 - Type of HCP seen during outpatient visits
- Proportion of patients with at least one interaction with CNS
- Number of CNS interactions per patient
- Type of CNS interaction
- Reason for CNS interaction
- Proportion of patients with at least one interaction with AOS
- Number of AOS interactions per patient
- Type of AOS interaction
- Reason for AOS interaction

For the estimation of endpoints, *the following definitions will be implemented. PFS will be defined as the time from the date of palbociclib initiation to the date of first documented disease progression (as documented in the radiological assessment section of the eCRF) or death. OS will be defined as the time from the date of palbociclib initiation until death from any cause. Time to achieving best overall response will be defined in patients who respond to treatment as the time from the date of palbociclib initiation until*

PFIZER CONFIDENTIAL

achievement of the best overall response: CR, or PR if CR is not achieved during follow-up. Duration of response will be defined as the time from the date CR or PR was first documented (whichever is recorded first) to the date of first documented disease progression or death from any cause (whichever occurs first).

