8.1.3 Analysis for binary endpoints

Most binary endpoints will be summarised using frequency tables with percentages. For survival-related endpoints, Kaplan-Meier analysis may be used with proportions of patients reaching an event after different time periods and median survival (the time at which 50% of patients have reached a given endpoint out of all patients that are still being followed-up at that point or have reached that given end point) with 95% confidence intervals estimated using the method of Brookmeyer and Crowley⁶ or another appropriate method⁷. Swimmer plots will be used to show individual patient response to treatment over time (CR, PR, stable disease, progressive disease); these are plots that display a range of information with bars indicating the length of follow-up for each individual patient and symbols on the bars showing where CR and PR are reached and end.

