prescribed treatment in the 1st, 2nd, and 3rd line after palbociclib discontinuation was presented as a categoric variable as per section 8.1.2. Dose, duration of subsequent treatments and number of completed 28-day cycles per patient were presented as quantitative variables as per section 8.1.1. Number of completed 28-day cycles (categories: 1-6 cycles, 7-12 cycles, 13-18 cycles, 19-24 cycles, 25-27 cycles and No completed cycles) and the proportion of patients co-administered letrozole or fulvestrant were presented as categoric variables as per section 8.1.2. All other endpoints were evaluated as proposed.

8.2.3 Secondary Objective 2: To describe overall survival and progression-free survival, response (CR, PR), stable disease. This includes estimating the proportion of patients achieving those endpoints at 1 and 2 following palbociclib initiation: median survival, time to response and duration of response. In patients who respond to treatment, to describe PR and CR using “swimmer plots”.

Proposed: For the estimation of the proportion of patients alive, and free from disease progression, the denominator will be all patients known to be alive at the selected time-points (e.g., 1 years, 2 years, and 3 years). For the estimation of the proportion of patients achieving PR, CR and with stable disease at the selected time-points (1 years and 2 years), the denominator will be all patients with at least one assessment of response (CR / PR / no response or stable disease / progressive disease) in the past year.

[figure not shown]
Actual: Proportion of patients free from disease progression, are alive, achieved PR, CR or stable disease were analysed separately at the 2-year timepoint only. Length of follow-up, and time to best response and first response were presented as quantitative variables as per section 8.1.1. Best response to palbociclib, overall and by de novo and relapse status was treated as a categoric variable and analysed according to section 8.1.2.

8.2.4 Secondary Objective 3: To describe the occurrence of neutropenia during the first-year post-initiation observation period.

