Describing treatment patterns 1,2 and 3 years after palbociclib initiation	Full Analysis set	Secondary Objective 1	Overall and Treatment Line	Frequency tables and percentages for proportions of patients completing a 28-day cycle, co-administered letrozole and fulvestrant at palbociclib initiation. Summary statistics calculated (incl. Mean/Median/SD/IQR/Range) for number of completed 28-day cycles	Excluded
Proportion of patients free from disease progression	Full Analysis set	Secondary Objective 2	Overall and Treatment Line	Frequency tables and percentages	Excluded
Proportion of patients alive	Full Analysis set	Secondary Objective 2	Overall and Treatment Line	Frequency tables and percentages	Excluded
Proportion of patients achieving PR/CR/with stable disease	Full Analysis set	Secondary Objective 2	Overall and Treatment Line	Frequency tables and percentages	Excluded
Median PFS	Full Analysis set	Secondary Objective 2	Overall and Treatment Line	Kaplan-Meier analysis, median PFS measured as being time from the date of palbociclib initiation to the date of first document disease progression or death. 95% confidence intervals calculated for median.	Standard imputation for dates (section 7), otherwise exclude.
Median OS	Full Analysis set	Secondary Objective 2	Overall and Treatment Line	Kaplan-Meier analysis, median OS measured as being time from the date of palbociclib initiation to the date of death. 95% confidence intervals calculated for median.	Standard imputation for dates (section 7), otherwise exclude.
Median time to best overall response (CR or PR)	Full Analysis set	Secondary Objective 2	Overall and Treatment Line	Kaplan-Meier analysis, time to first best overall response (partial/complete response) measured as being time from the date of palbociclib initiation to the date of first response. 95% confidence intervals calculated for median.	Standard imputation for dates (section 7), otherwise exclude.
Swimmer plots	Full Analysis set	Secondary Objective 2	Overall and Treatment Line	Swimmer plots used to represent patient response (CR / PR/ stable disease / progressive disease) to treatment for patients responding to treatment (CR or PR).	
Duration of response (PR/CR)	Patients enrolled achieving PR/CR	Secondary objective 2	Overall and Treatment Line	Kaplan-Meier analysis, median duration of response measured as being time from the	Standard imputation for dates (section 7),

PFIZER CONFIDENTIAL

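### Landmark proportions alive and progression-free are taken over patients known to be alive, so the first is always 100% and the second leaves out every death

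*Protocol*

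**What the plan says.** Protocol 9.3 lists being free from progression and being alive as two separate items at 1, 2 and 3 years. SAP 6 keeps them separate, at 2 years, under "Proportion of patients at 2-years following initiation of palbociclib who". SAP 8.2.9 gives "Proportion of patients alive" its own row, apart from the progression-free row.

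Protocol 9.7 sets one denominator for both: for the "proportion of patients alive, and free from disease progression, the denominator will be all patients known to be alive at the selected time-points". SAP 8.2.3 repeats it under 'Proposed': "the denominator will be all patients known to be alive at the selected time-points". The 'Actual' paragraph of SAP 8.2.3 says that the proportions "were analysed separately at the 2-year timepoint only" and does not mention a denominator.

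Three other places bear on the point:

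- SAP 8.2.9 assigns both proportions to the Full Analysis Set, to be shown as counts and percentages with missing data excluded. It assigns Kaplan-Meier to the medians, not to these rows.
- SAP 8.1.3 allows a time-to-event route without requiring it: "For survival-related endpoints, Kaplan-Meier analysis may be used".
- Protocol 9.3 counts death as a PFS event. So does SAP 6, where PFS runs to first documented progression ("as documented in the radiological assessment section of the eCRF) or death").

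**The concern.** A landmark survival proportion needs the patients who died in its denominator. If only patients known to be alive are counted, everyone in the denominator is also in the numerator, and the result carries no information.

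The progression-free percentage is the greater risk. A row showing 100% alive would be noticed, but a survivors-only progression-free percentage looks plausible. Patients who died are in neither its numerator nor its denominator, so it would not agree with the Kaplan-Meier PFS curve drawn from the same patients. With complete follow-up the error is in the favourable direction. The rule also drops living patients whose status at the landmark is unknown, which adds a selection of unknown direction.

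These are the landmark results for OS and PFS in a study that, by Protocol 7, may support assessments of benefit in routine care. Quality control may not catch the problem: Protocol 9.8 limits independent analysis review to the primary endpoint and plans no further checks.

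**Working it through.** The plan gives no landmark figure to reproduce. The study is descriptive and its size is pragmatic, so the check is algebra followed by an illustration.

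**Algebra, complete follow-up.** Let N be all patients, D the deaths by time t, and F the patients alive and progression-free at t.

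- Proportion alive under the rule: (N − D)/(N − D) = 100%. Over all patients it is (N − D)/N = OS(t).
- Progression-free under the rule: F/(N − D) = PFS(t)/OS(t). Over all patients it is F/N = PFS(t).
- The rule therefore multiplies the progression-free proportion by 1/OS(t): 1.11 at OS 90%, 1.25 at 80%, 1.43 at 70%.

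**Inputs for the illustration at 24 months.**

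- Median PFS of 24.8 and 20.2 months, from the two first-line trials quoted in Protocol 7.
- Exponential PFS (assumption).
- 24-month OS of 70% to 90% (assumption; the documents give none).
- No loss to follow-up (assumption).

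PFS(24) = exp(−ln 2 × 24/median), which is 0.511 for 24.8 months and 0.439 for 20.2 months.

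| Median PFS | PFS(24) | OS 70% | OS 75% | OS 80% | OS 90% |
|---|---|---|---|---|---|
| 24.8 months | 51% | 73% | 68% | 64% | 57% |
| 20.2 months | 44% | 63% | 59% | 55% | 49% |

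The four right-hand columns are the values reported under the rule, PFS/OS. The excess is 5.7 to 21.9 percentage points for the 24.8-month median and 4.9 to 18.8 for the 20.2-month median.

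In patient numbers, take about 200 patients (SAP 2.1), the 24.8-month median and OS 75%. Then 102 are progression-free and 150 are alive. The rule gives 102/150 = 68%; all patients give 102/200 = 51%.

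**Could loss to follow-up cancel the inflation?** Suppose a fraction x of living progression-free patients is lost and no living progressed patient is lost. The reported value is PFS(1 − x)/(OS − x·PFS). Setting this equal to PFS gives x = (1 − OS)/(1 − PFS).

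- Median 24.8 months: x = 0.30/0.489 = 61% at OS 70%, and 0.10/0.489 = 20% at OS 90%.
- Median 20.2 months: x = 0.30/0.561 = 53% at OS 70%, and 0.10/0.561 = 18% at OS 90%.

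Cancellation is possible, but it needs substantial loss confined to the patients who are doing well.

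**The case against.** **The rule may not be operative.** SAP 8.2 notes that some proposed analyses were not carried out and that their text is kept as a record. In the SAP the rule appears only under 'Proposed'. The 'Actual' text of 8.2.2 closes by saying that the remaining endpoints followed the proposal, and the 'Actual' text of 8.2.3 has no such sentence. SAP 8.2.9 names the Full Analysis Set, and Protocol 9.7 lets the SAP modify the protocol. This stands in part: the documents do not show which denominator was used, and the 2-year figures may be sound. But the note covers analyses that were not conducted, and 8.2.3 says that these proportions were. Their only stated denominator is the survivors-only one, and nothing withdraws it.

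**The progression-free share among survivors is a legitimate conditional description, not a wrong PFS estimate.** It could be reported under that label. However, the objective names OS and PFS and then asks for the proportion of patients achieving those endpoints, so a survivors-only share is not the quantity sought. This defence also does nothing for the proportion alive. Reading the two as one joint proportion does not fit the separate listings, and deaths would still be left out.

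**The numbers are hypothetical.** This is fair. OS at 24 months is assumed, and the trial medians are first-line while SAP 5.4 includes second- or later-line patients. The 100% result and, with complete follow-up, the factor 1/OS(t) do not depend on these assumptions.

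**The study is descriptive and the endpoint secondary.** Also true, and the Kaplan-Meier medians are untouched. That limits the reach of the error but does not make the rule defensible.

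The aim in Protocol 9.1 to "avoid bias arising from exclusion of deceased patients" explains how records of deceased patients are accessed. It concerns entry into the cohort and is not relied on here.

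**Conclusion.** The concern holds and the text must be corrected. As written, one named endpoint is fixed at 100% whatever the data, and the other is conditional on survival, although the objective asks for PFS and death is a PFS event. Both follow from the wording alone.

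The size of the second effect depends on mortality and on loss to follow-up. Under the stated assumptions it is roughly 5 to 22 percentage points too high at 24 months. Differential loss could reduce or cancel it. Whether any reported figure is wrong cannot be told from the documents.

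**What to change.** - In Protocol 9.7 and SAP 8.2.3, delete the denominator of patients known to be alive for these two proportions.
- In SAP 8.2.3 and 8.2.9, specify Kaplan-Meier OS and PFS probabilities with 95% confidence intervals, from the index date, on the Full Analysis Set, at each landmark analysed. That is 2 years in the current SAP, plus 1 and 3 years if they are reported. Censored patients then contribute up to their censoring date, under the usual assumption of non-informative censoring.
- In SAP 8.1.3, make Kaplan-Meier mandatory for these proportions instead of optional.
- In the 'Actual' text of SAP 8.2.3, state which denominator was used. If it was the survivors-only one, rerun the landmark figures.

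No new data are needed, because the OS and PFS curves are already planned. The cost is a text change and, if the old denominator was used, a minor reanalysis whose percentages will probably be less favourable.

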7. RATIONALE AND BACKGROUND

BC is the most frequently occurring cancer in women and is a major public health problem, with 1.7 million new cases diagnosed globally in 2012, representing 25% of all incident cancer cases (1). In Europe, more than 464,000 new cases of BC were diagnosed in 2012. The UK incidence rate is the sixth highest in Europe, with around 54,900 new BC cases every year (2). HR+ BC represents the largest therapeutic subtype of the disease and accounts for over 80% of cases in the UK (4).

Annually, approximately 6-7% of new BC cases present as *de novo* metastatic disease and approximately 30% of women with early BC go on to develop metastatic disease (2). Survival from BC largely depends on the stage at diagnosis; the 1-year survival is 100% for patients diagnosed at stage I, versus 63% for patients diagnosed at stage IV; and five-year survival is 99% and 15% respectively for stage I and IV (5,6).

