Secondary objective: To describe overall survival and progression-free survival, response (CR, PR), stable disease. This includes estimating the proportion of patients achieving those endpoints at 1, 2 and 3 years following palbociclib initiation; median survival, time to response and duration of response. In patients who respond to treatment, to describe PR and CR using "swimmer plots".

 Proportion of patients at 1, 2 and 3 years following initiation of palbociclib who: 
 Are free from disease progression. Are alive Achieved PR Achieved CR Had stable disease Median (95% confidence interval [CI]) : 
 PFS OS Time to achieving best overall response Summary measures of duration of response (Kaplan-Meier analysis). Representation of all radiological assessment of response (CR / PR / no response or stable disease / progressive disease) in patients responding to treatment (achieving CR or PR following initiation of palbociclib) using “swimmer plots”. 	
 Date ((DD/MM/YYYY) unless specified otherwise) of start and end of palbociclib. Date of data collection. Patient status at the end of data collection period (alive/dead): 
 Date of death / last clinic visit. If not known (i.e. lost to follow-up), date of last recorded hospital visit. Radiological assessments of response during the follow-up period: date of assessment and outcome (CR / PR / no response or stable disease / progressive disease), as documented by the local investigator.

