8 STATISTICAL METHODOLOGY AND STATISTICAL ANALYSES

8.1 STATISTICAL METHODS

[figure not shown]
The following statistical methods will be used:

Full analysis will be conducted on 2-year follow up data not 3-year follow up data.

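### The 2-year response proportions count only patients assessed in months 12–24, which drops year-1 deaths and overstates CR/PR relative to all treated patients

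*Protocol*

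**What the plan says.** The endpoint in Protocol 9.3 is the "Proportion of patients at 1, 2 and 3 years following initiation of palbociclib who" are progression-free, are alive, achieved PR, achieved CR or had stable disease. The underlying data are "Radiological assessments of response during the follow-up period: date of assessment and outcome", as the local investigator recorded them.

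For the three response categories, Protocol 9.7 states that "the denominator will be all patients with at least one assessment of response"; the sentence ends "progressive disease) in the past year". A separate denominator is given for the alive and progression-free proportions.

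SAP 8.2.3 repeats the response denominator under *Proposed*, for 1 and 2 years. Under *Actual* it says that the proportions "were analysed separately at the 2-year timepoint only", and gives no denominator. SAP 6 likewise lists the "Proportion of patients at 2-years following initiation of palbociclib who" fall in each category, and SAP 8.1 adds: "Full analysis will be conducted on 2-year follow up data not 3-year follow up data".

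SAP 8.2.9 assigns the outcome to the full analysis set, analysed by frequency tables with missing data excluded. SAP 5.1 defines that set to include deceased patients.

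**The concern.** At 2 years, a look-back of one year means months 12–24. Three things follow.

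- A patient who progressed and died at month 10 is in neither numerator nor denominator, although that patient's 2-year status is known: not in response.
- A patient alive but not assessed in months 12–24 also disappears.
- A patient with PR at month 13 who died at month 18 has an assessment in the window. No text requires being alive at the landmark, so this patient can be counted as PR at 2 years.

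The table row is labelled as the full analysis set, but the percentage describes a subset selected partly by surviving the first year. This also undoes a precaution taken elsewhere. Protocol 9.1 has care teams extract deceased patients' records so that leaving them out does not bias the results. Protocol 9.9 relies on Kaplan–Meier methods to deal with attrition, including for CR and PR, but these proportions are plain percentages and get no such protection.

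**Working it through.** **Plan's own figure.** There is none to reproduce. The documents give no expected response rate, death rate or assessment rate for this cohort, and the sample size is pragmatic (about 250 in the protocol, about 200 consented in SAP 2.1).

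**Which landmarks are affected.** At 1 year the look-back reaches the index date. A patient assessed and then dead by month 10 stays in the denominator, and only never-assessed patients are lost. At 2 years, and at 3 years if analysed, earlier deaths are lost.

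**Notation (all values assumed).** d = share who died before month 12; u = share alive but unassessed in months 12–24; p = response rate in assessed patients; q = response rate in living unassessed patients. A patient who died in months 12–24 without an assessment in the window has the same effect as one in d.

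**Formulas.**
- Reported proportion = p.
- All-treated proportion = p(1−d−u) + q·u.
- If q = p: reported / all-treated = 1/(1−d).
- If q = 0: reported / all-treated = 1/(1−d−u).
- The reported figure is too high whenever q < p(1 + d/u).

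**Numbers.** Take 200 treated patients with 60 in response at 2 years, all of them assessed, so that the all-treated figure is 60/200 = 30.0%. The third and fourth columns take q = 0.

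| d | u | Denominator | Reported | Factor, q = 0 | Factor, q = p | q/p needed to reverse |
|---|---|---|---|---|---|---|
| 5% | 0 | 190 | 31.6% | 1.05 | 1.05 | – |
| 5% | 20% | 150 | 40.0% | 1.33 | 1.05 | 1.25 |
| 10% | 10% | 160 | 37.5% | 1.25 | 1.11 | 2.00 |
| 20% | 20% | 120 | 50.0% | 1.67 | 1.25 | 2.00 |

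The percentages do not depend on cohort size.

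**Bounds for unknown status, d = u = 10%.** Of 200 patients, 20 are dead, 20 are unknown, and 160 are assessed with 60 in response. The all-treated proportion is 60/200 = 30.0% if no unknown patient is in response and (60+20)/200 = 40.0% if all are. At q = p it is (60+7.5)/200 = 33.75%, and 37.5/33.75 = 1.11, as the formula gives.

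**Simulation.** Three scenarios on assumed inputs, with deaths by month 12 of 4.0%, 6.6% and 16.2%, took status at the last assessment in months 12–24 as the numerator. The rule gave 37.2%, 39.3% and 34.5%; the same patients over all treated gave 33.7%, 32.2% and 22.3%. With an ever-responded numerator the rule gave 49%–53% against 38%–48%. The direction was upward throughout.

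**The case against.** **The SAP may not have used this rule.** The denominator appears only under *Proposed*, and SAP 8.2 says some proposed analyses were dropped and kept as a record. The sentence that other endpoints were evaluated as proposed belongs to 8.2.2, not 8.2.3. This stands as a caution: use of the rule in the final tables is inferred. It is nonetheless the only denominator written anywhere, and it is still in the protocol.

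**Numbers analysed and missing counts will be shown** (Protocol 9.7, SAP 7), with PFS, OS and best response alongside. That lets a reader see part of the loss but does not change the percentage. Death before month 12 is also a known outcome, not a missing value.

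**The rule does not keep only patients doing well.** Correct: progressive disease is an assessment outcome, so patients found to have progressed in year 2 stay in.

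**All-treated denominators have their own bias.** Also correct. If unknown status is silently counted as non-response, the figure is biased downward, so the remedy must show it separately.

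**A much larger effect might be inferred** from the "63% for patients diagnosed at stage IV" that Protocol 7 quotes for 1-year survival: 37% mortality would turn 30% into 30/0.63 = 47.6%. That is a general background figure for stage IV breast cancer, not one for this cohort. The same section gives median PFS of 24.8 and 20.2 months with palbociclib plus letrozole in two first-line trials. Under an exponential assumption, progression or death by month 12 is 1 − 2^(−12/24.8) = 28% and 1 − 2^(−12/20.2) = 34%, and deaths alone would be fewer. The 37% is not a usable forecast.

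**Conclusion.** The point holds for the 2-year landmark, and for 3 years if it is analysed. Against all treated patients, the proportion in CR/PR is overstated by 1/(1−d) if living unassessed patients respond like assessed ones: 1.05, 1.11 and 1.25 for d of 5%, 10% and 20%. It is overstated by 1/(1−d−u) if none of the unassessed is in response. The direction would reverse only if unassessed patients responded more often than assessed ones by more than the factor 1 + d/u. Counting as in response someone who died after a year-2 assessment is a further, separate error. Every d, u and response rate here is an assumption, so the size is illustrative.

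Four stronger readings are not supported:

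- **That every landmark loses early deaths.** The 1-year window covers all follow-up.
- **That stable disease is overstated in the same way.** The plan does not say whether the numerator is status at the landmark or ever achieved, and for stable disease the upward direction is clear only for status at the landmark.
- **That inflation is worse in a poorer-prognosis treatment line.** It would rise with early mortality, but the documents give no mortality by line for this cohort.
- **That best response has a different denominator.** Its denominator is not stated.

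This is a secondary endpoint in a descriptive study, and the correction is worth making because the bias comes from a written rule and is cheap to remove.

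**What to change.** In Protocol 9.7, SAP 8.2.3 and the matching row of SAP 8.2.9:

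1. Define the numerator as response status at the landmark in patients alive on that date.
2. Use all treated patients as the denominator.
3. Count patients who died or progressed before the landmark as not in response.
4. Show status unknown as its own row, and give the proportion with that row taken first as all not in response and then as all in response.
5. Keep the assessed-only proportion, if wanted, as a supplement labelled 'among patients assessed in months 12–24'.
6. State in the *Actual* text which denominator was used for the figures already produced.

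Death, progression and assessment dates are already in the dataset (Protocol Annex 3, SAP 11), so the cost is wording and some extra tabulation. The downside is that the reported proportions will probably be lower.
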